If applicable, indicate which procedures may have risks to an embryo or fetus should the subject be or become pregnant.

If applicable, describe risks to others who are not subjects and risks to Kaiser Permanente.

b. Potential Benefits to Subjects

Describe the potential benefits that individual subjects may experience from taking part in the research. Include the probability, magnitude, and duration of the potential benefits.

Indicate if there is no direct benefit. Do not include benefits to society or others.

Note: Compensation is not considered a benefit and should not be included in this section. See Compensation to Participants section.

11. Costs to Participants

Describe any costs that participant may be responsible for due to participating in this study (for example, co-pays; paying for treatment, therapies, or other interventions, or the delivery of these) and how you will inform participants of these costs prior to their enrollment in this study.

12. Compensation to Participants

Describe any compensation provided to participants, for example, for time inconvenience, discomfort, travel, or in the event of research related injury.

If applicable, describe how you will inform participants of this prior to their enrollment in the study, including if payment will be prorated if the subject withdraws early from the study.

Note: payment may not be withheld as an incentive for participants to complete the study.

13. Resources Available (delete if not applicable)

Describe any special resources or expertise required to conduct the study.

14. Drugs or Devices (delete if not applicable)

If the research involves drugs or devices and is investigator-initiated, indicate whether there is any possibility that the results will be reported to FDA (e.g. as part of a new drug application [NDA] or premarket approval application [PMA]).

If this is a device study and you think the device is Non-Significant Risk, include justification here or upload it as a separate document along with any available device information (instructions for use, etc.).

If the drug is investigational (has an IND) or the device has an IDE or a claim of abbreviated IDE (Non-Significant Risk device), confirm that you will comply with all applicable FDA requirements for investigators. Also see the [ICH-GCP guidance](#) for a summary of investigator and sponsor responsibilities in clinical trials.

Address the items listed below as applicable.

Drug Studies:

- *Confirm that you will follow applicable KP pharmacy policies and procedures.*
- *Describe your plan for drug storage, handling, and accountability, including distribution, return, and destruction of the drug(s).*
- *If applicable, upload a copy of the Investigator Brochure for each drug. (If this is not an Oncology study, you must also send an additional copy to the Regional Formulary and Therapeutics Committee.)*

Device Studies:

- *Describe the device, the manufacturing process, and the device labeling, including safety instructions or warnings. If available, this may be addressed in separately uploaded device information (such as instructions for use).*
- *Describe device storage, handling, and accountability, including how access to the device will be limited to appropriate personnel and how you will ensure the device will be used only for appropriate study subjects.*

15. Multi-Site Coordination (delete if not applicable)

If this site will be the coordinating center for any activities, describe those activities here or in a separate document.

Describe the processes to ensure communication among sites, such as:

- *All sites have the most current version of the protocol, consent document, and HIPAA authorization.*
- *All required approvals have been obtained at each site (including approval by the site's IRB of record).*
- *All modifications have been communicated to sites, and approved (including approval by the site's IRB of record) before the modification is implemented.*
- *All engaged participating sites will safeguard data as required by local information security policies.*
- *All local site investigators conduct the study appropriately.*
- *All non-compliance with the study protocol or applicable requirements will be reported in accordance with local policy.*
- *Communication of problems, interim results, and study closure.*

16. Community-Based Participatory Research (delete if not applicable)

Describe involvement of the community in the design and conduct of the research.

Describe your plan for ensuring that community research partners are appropriately trained in human subjects protection.

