Protocol

SPREAD-NET: PRactices Enabling Adapting and Disseminating in the Safety NET

NCT02325531

6/2/2016

INSTRUCTIONS:

- **All sections are required.** If a section does not apply to your project please enter "N/A." The level of detail required for each section will vary with the complexity of your project.
- If your study has multiple aims, break each section down to address each aim of the study, as appropriate.
- **Delete all instructions (italics).**
- See the [Research Compliance](#) website for guidance and information on a number of topics including vulnerable populations, consent, inclusion of non-English speakers, genetic research, and data sharing.
- If you are doing a data-only study with no prospective or interventional components, use the **Data Only Protocol Template** instead.

1. Protocol Title

SPREAD-NET: Practices Enabling Implementation and Adaptation in the Safety Net

2. Objectives

We propose to compare the effectiveness of different 'support strategies' at helping diverse community health clinics (CHCs) sustainably implement an intervention shown to reduce patients' cardiovascular disease (CVD) event risk. Kaiser Permanente developed and implemented the 'ALL Initiative' (a.k.a. 'ALL'), a clinic-level intervention designed to increase rates of adult patients with diabetes mellitus (DM) or CVD who are prescribed cardio-protective medications (statins and ACE-Inhibitors) according to evidence-based guidelines. After ALL was shown to be highly effective in Kaiser Permanente's integrated care setting, our team demonstrated the feasibility of adapting it for successful implementation in 11 CHCs - with the help of substantial implementation support. The next step in this body of research is to identify the amount and type of support needed to effectively implement and sustain this intervention in a greater number of CHCs. To that end, we will conduct a trial in which 30 CHCs are cluster-randomized to receive low, medium, or high-intensity support in implementing ALL. We will conduct this work with CHC members of OCHIN, a community health information technology network that hosts one of the nation's largest CHC electronic health record (EHR) platforms; study CHCs share a single, linked EHR. Guided by the Practice Change Model and RE-AIM framework, we will use mixed-methods to:

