Disseminating successful interventions in diverse primary care settings could significantly improve the health of patients with DM / CVD nationwide. Yet few studies have focused on comparing effective strategies for supporting change in health care settings.^{5,79-91} **Thus an important barrier to the widespread dissemination of evidence-based interventions such as ALL is a lack of knowledge about the most effective strategies for supporting sustainable implementation in diverse care settings.**^{1,3,5,8-11,15,21,22,24,42,44,79-88,92-97} This limitation is particularly problematic for the Community Health Centers (CHCs) in our health care ‘safety net’,^{1,13,14} which care for millions of underserved patients, and are expected to serve millions more through the Affordable Care Act.⁹⁸⁻¹⁰⁰ Rapid, effective implementation of interventions shown to improve care delivery and health outcomes could ensure that CHC patients benefit from cutting-edge clinical knowledge. Although the need is well-acknowledged, we know of no previous randomized trial comparing strategies for supporting consistent, reliable implementation of evidence-based care in CHCs.^{7,10,12,101}

This study will address the lack of knowledge about effective implementation support strategies. We propose to compare the effectiveness of 3 replicable strategies for supporting the implementation of the ALL Initiative in CHCs. These strategies have been shown to be effective and feasible in CHCs. We will conduct a pragmatic trial in which 30 CHCs are cluster-randomized to receive low, medium, or high-intensity implementation support.

We propose to address an important barrier to such dissemination - the **lack of knowledge about the most effective strategies for supporting CHCs’ implementation of evidence-based interventions.**^{1,13,14,45,79-91,93} This work is positioned to have broad impact. Understanding how to efficiently support implementing the evidence-based ALL Initiative in CHCs could reduce CVD event risk in patients with CVD / DM nationwide, improving health outcomes and reducing care costs. While this project focuses on ALL in CHCs, we will discover generalizable strategies for implementing ALL in other primary care settings and also for supporting CHCs’ implementation of other interventions shown to improve CVD /DM outcomes, and other morbidities.

4. Study Design

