We will conduct a cluster-randomized, prospective, pragmatic trial with 3 arms (Figure 3). In months 1-18, we will collect baseline data via a survey of all study sites, and refine the toolkit. At the start of Implementation Year 1 (study month 19), 30 CHCs will be randomized to receive low, medium, or high-intensity support in implementing the ALL Initiative. Guided by RE-AIM and the Practice Change Model, we will use mixed methods to assess how effectively the different levels of intensity support intervention uptake, guideline-based prescribing, and patient health (Aim 1), and sustainability over 3 years (Aim 2). We will identify clinic-level factors associated with each support strategy’s effectiveness and sustainability (Aim 3), and adapt as possible. We will also conduct a cost analysis.

Arm 1 (‘Low’ intensity support) components: TOOLKIT. The point person will receive the implementation toolkit (paper and electronic form) at the start of Implementation Year 1. Toolkit components are ready for

use except as noted. EHR-based tools, built in OCHIN's EHR, will be activated at that time. The toolkit will include annual 1-hour 'Basic Webinars' open to the study point person, and hosted by the research team.

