b. Inclusion and Exclusion Criteria

Describe how individuals will be screened for eligibility and the criteria that define who will be included or excluded in your final study sample.

Describe the plan for disposition of data collected during recruitment/screening in the event of a screen failure or when a potential subject is contacted but declines participation (e.g. destroyed immediately, destroyed at end of study, retained for separate analysis or so that subjects are not contacted repeatedly about participation after they have declined, etc.)

Inclusion criteria.

Quantitative data: ~20,000 OCHIN patients from 30 clinics. Data will be extracted monthly from OCHIN's EHR including (a) Study population identification (age, CVD / DM, prescriptions); (b) Patient and (c) Clinic characteristics; (d) Patient outcomes (last BP, LDL results and measurement dates; issued prescriptions and dates); and (e) Process measures (e.g., tool use, encounters). (f) Cost analysis data will be collected as well.

Qualitative data: Ongoing phone calls with 30 point people. Site Visits: 18 visits in total. Breakdown: 6 clinics per year X 3 years. Interviews: 208 in total. We anticipate 108 formal (Breakdown: 6 clinics X 18 interviews) and 100 telephone (6 clinics X 12 interviews, plus 28 follow-up interviews).

Exclusion. Pregnant and lactating women will be excluded, as the ALL medications are contraindicated for pregnancy.

c. Vulnerable Populations

Regulatory Categories: Indicate whether you will include or exclude each of the following populations. This refers to subjects who are known members of these populations upon recruitment or at any time during the study. You may not include members of these populations unless you describe this in your inclusion criteria.

- Children
- Pregnant women
- Neonates of uncertain viability or nonviable neonates (up to 28 days post birth)
- Prisoners (NOTE: The KPNW IRB does not have the appropriate membership to review research involving prisoners. Consultation with KFRI will be required.)

Justify the inclusion of any of these populations. Describe additional safeguards to protect the rights and welfare of these subjects.

Neonates (i.e., newborns) of uncertain viability or nonviable: Exclude
Children: Exclude

Decisionally/cognitively impaired: Include

Economically/educationally disadvantaged: Include

Non-English Speakers: Include

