Employees who are specifically and intentionally targeted to be included in this study population because of their workplace and/or employee status: Include

Elderly: Include

Prisoners: Prisoners are excluded or not anticipated to become study subjects

d. Setting

Describe the sites or locations where your research team will conduct the research.

If this is a multi-site study:

- Specify what procedures are being performed at this site or by this site's personnel (consider recruitment, consent process, study procedures, data analysis, etc.).
- State how each site will satisfy its IRB review requirements. Indicate if you are asking this site's IRB to rely on another IRB or if another institution would like to rely on this site's IRB and include this information in the eIRB IRQ.

OCHIN member clinics (29 total): Winding Waters, Scappoose / OHSU, Santa Cruz County, Mosaic, Community HealthNet, Progressive Community Health Center, Truckee Tahoe Medical Group, Monterey Health Department, La Pine, Placer County, SW Montana, Neighborhood Family Practice

Michigan State University (MSU)

Mid-Atlantic Permanente Research Institute (MAPRI) – KPMAS

e. Recruitment Methods

Describe in detail how study participants will be recruited and enrolled. For example, will you openly recruit through the use of advertisements, websites, or brochures? Will you do targeted recruitment through the use of existing records or referral? If you will contact potential participants for recruitment, include the method(s) of contact and number of contact attempts that may be made.

Upload in the eIRB all recruitment materials, including brochures, advertisements, mailings, scripts, and website materials (screen shots). Note: If your materials are yet to be developed, these must be submitted to the IRB as a modification request and approved prior to use with study participants.

Describe, by position / title, who will be recruiting and enrolling participants (providing the particular names of research team members is not necessary).

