Investigators sometimes plan to re-contact and re-recruit participants for future follow-up studies. That is, investigators may anticipate that participants for a currently proposed study will be logical participants in a future study. If there are any such expectations or plans for the participants in the currently proposed study to be re-contacted for follow-up studies, describe this. (And, note that participants should be informed of this potential for re-recruitment during the current study's consent process.)

Clinic recruitment will be led by [name] (Co-I) at OCHIN. [name] will follow-up with each clinic (who agreed to participate in the study during the proposal stage) by sending them an introductory email, FAQ handout and MOU. Patient data will be identified by the OCHIN DM registry. Staff and providers will be recruited by each OCHIN clinic's point person, specifically looking for local opinion leaders and / or as having strong positive or negative feelings about the intervention and support strategies used.

f. Consent Process

Describe how you will obtain and document consent, including:

- *Where, when and how the consent process will take place.*
- *A process to ensure ongoing consent.*
- *Steps that will be taken to minimize the possibility of coercion or undue influence.*
Any steps that will be taken to ensure the subjects' understanding.

This research will use a consent procedure which does not include, or which alters, some or all of the elements of informed consent; or waives the requirement to obtain informed consent in its entirety. We are requesting a waiver of informed consent in its entirety for the quantitative and qualitative aspects of this study.

All of the following four statements are true: The research involves no more than minimal risk to the subjects; The waiver or alteration will not adversely affect the rights and welfare of the subjects; The research could not practicably be carried out without the waiver or alteration; and Whenever appropriate, the subjects will be provided with additional pertinent information after participation.

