Specific Aim 1 & 2 analyses. For Aim 1, we will use an interrupted time-series design with three-level hierarchical linear models to assess differences in the impact of the intervention's implementation, across the 3 support strategies, on quantitative outcomes (patient health [Effectiveness], guideline-based prescribing [Reach]). This method is commonly used to compare changes in rates across time pre- and post- implementation. Time in monthly intervals will form the 1st level of the model, person the 2nd, and clinic the 3rd; these models do not require patient-level data at all time points. We will include a dummy-coded variable for study arm (reference group = 'High'-intensity support) and clinic level covariates (as guided by the Practice Change Model components) at model level-3, and patient level covariates at level-2. The level-1 model will be specified as a segmented regression model, to yield an estimate of the level and slope across time of rate of the outcomes of interest in the 2 years pre-implementation, and changes in the level and slope of these rates in the 12 months post-implementation. Change in level provides an estimate of the immediate effect of the intervention. Change in slope gives an estimate of effect across time. We will include a cross-level interaction of study arm with time, change in level, and change in slope; the interaction of change in slope by study arm tests if the change from pre to post intervention in the trends in the rates over time differs across arms. Similarly, the interaction of change in level by study arm tests if the immediate effect of the intervention differs across study arms. Separate analyses will be conducted for percent of patients with guideline-appropriate prescriptions for ACE/ARBs, statins (our primary outcomes), and with last BP under control, and last LDL under control (secondary outcomes) (Table 5). Aim 2 analyses will use the same approach, adding time points through 36 months post-intervention [Maintenance]. The time period variable will have 3 levels (pre-intervention, 12 months post-, and 13-36 months post-intervention). Of interest is whether the slopes (rate of change) or level in the last time period differ across the 3 arms.

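### Does listing 29 clinics under 12 names mean that the clinic is the wrong top level for the analysis model?

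*Combined protocol and SAP*

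**What the plan says.** Section 4 (Study Design) states that "30 CHCs will be randomized to receive low, medium, or high-intensity support in implementing the ALL Initiative". Section 7.a (Specific Aim 1 & 2 analyses) sets out a three-level model: "Time in monthly intervals will form the 1st level of the model, person the 2nd, and clinic the 3rd". There is no level above the clinic.

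Section 5.d (Setting) introduces its site list with "OCHIN member clinics (29 total" and then gives 12 names (13 if the entry with a slash is two), so at least one name covers several clinics. Clinics per name are not given.

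Other sections describe the unit indirectly. Section 5.b refers to "OCHIN patients from 30 clinics" and to "Ongoing phone calls with 30 point people". Section 5.e says that the recruitment lead "will follow-up with each clinic (who agreed to participate in the study during the proposal stage" at an earlier stage. Section 6 has one point person for each clinic. CHC is expanded in two ways: Section 2 speaks of "helping diverse community health clinics (CHCs) sustainably implement an intervention", and Section 3 calls the evidence gap "particularly problematic for the Community Health Centers (CHCs) in our health care" safety net.

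The readable text contains no rule on stratification, blocking or the handling of clinics that share a name. Section 4 refers to a Figure 3, and Section 3 puts an asterisk on the abbreviation CHC. Neither the figure nor the note is available here, so the most that can be said is that the rule was not found.

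**The concern.** In a cluster-randomised trial the unit of allocation determines which standard errors and degrees of freedom are valid. If each name is a parent organisation, and all clinics of an organisation went to the same arm, then about 12 units were randomised rather than 29 or 30. Clinics of one organisation may share leadership and policy, so their changes over time may be correlated. A model that stops at the clinic would then treat correlated clinics as independent. Its arm contrasts would be too liberal, and the power in Section 7.a would be too high. Every Aim 1 and Aim 2 arm comparison comes from this model, and the threshold regression in Section 7.a also classifies clinics. The two expansions of CHC, one suggesting a site and the other a larger body, add to the doubt.

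**Working it through.** **1. Which unit does the text describe?** There are 30 randomised CHCs, 30 clinics and 30 point people. In Section 6 the site-visit paragraph uses clinics and CHCs interchangeably: six clinics a year are visited, and the sites are chosen from among the CHCs. In Section 4 the Arm 2 components go to CHCs, whose trainee then trains staff at that person's own clinic. The double expansion of CHC does not help the 12-unit reading either. If CHC meant a parent organisation, there would be 30 organisations, not 12. Reaching 12 needs a grouping rule that is nowhere stated.

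**2. Which unit does the plan's power imply?** Inputs from the documents: statins 60% v 68% (the smallest difference), ICC .01 or .02, alpha .05, and about 20,000 patients in 30 clinics, which is 667 per clinic. Assumptions: equal arms (10 clinics, about 6,667 patients each) and a two-sided test.

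- Effective patients per arm: n = k·m / [1 + (m − 1)·ICC].
- Power = Φ{ [|p1 − p2| − 1.96·√(2p̄(1 − p̄)/n)] / √([p1(1 − p1) + p2(1 − p2)]/n) }.

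| Clusters per arm | n, ICC .01 | Power | n, ICC .02 | Power |
|---|---|---|---|---|
| 10 clinics of 667 | 871 | .936 | 466 | .721 |
| 11 clinics of 606 | 946 | .953 | 509 | .758 |
| 4 organisations, all clustering at that level | 378 | .630 | 194 | .375 |
| Plan's lower ends | | .95 | | .76 |

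The plan's figures need about 10 to 11 independent clusters per arm. The .76 is not exactly recovered with 10, but that is a separate small discrepancy. Using 29 clinics instead of 30 gives .929 and .707.

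**3. Clinics randomised singly.** A stand-in simulation used one change score per clinic, 29 clinics, 12 organisations, three arms, a pooled t test on 26 df and 60,000 runs per setting. The organisation's share of between-clinic variance was assumed to be 0, 10, 25 or 50%. Two layouts were assumed: near-even (seven names with 2 clinics, five with 3) and uneven (10, 6, 3, 2 and eight single clinics). Type I error was .048 to .051 in every setting. A separate simulation of single-clinic allocation stratified by organisation gave .05 at share 0 and lower values as the share rose (about .02 at 50%), so the test is then conservative.

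**4. Clinics under one name kept together (hypothetical).** Same stand-in, four organisations per arm, clinic-level test:

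| Share | 0 | 10% | 25% | 50% |
|---|---|---|---|---|
| Near-even | .050 | .069 | .100 | .155 |
| Uneven | .049 | .081 | .133 | .215 |

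For power with share λ at organisation level, 1/n = λ·ICC/4 + (1 − λ)·ICC/(29/3) + (1 − ICC)/6,667. For λ = 0, .5 and 1, power is .929, .769 and .630 at ICC .01, and .707, .493 and .375 at ICC .02 (normal reference, near-equal organisations).

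**5. Cost of guarding against step 4 by default.** Suppose clinics were kept together but organisations do not differ in change. For an effect of 1.30 between-clinic SD, analysing unweighted organisation means on 9 df lowers power from .78 to .70 (near-even) or from .70 to .48 (uneven), with no gain in validity. If clinics were randomised singly, one organisation can have clinics in several arms, and the organisation is then not the unit of allocation at all.

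**The case for a change.** The strongest case for acting is that the phrases favouring the clinic describe recruitment and contact, not allocation. The listed count (29) does not even match the randomised count (30), and a single sentence would remove a doubt that bears on every arm comparison. If clinics were in fact kept together, the inflation in step 4 is real, and the simulated error rates were reproduced in an independent run.

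Part of this stands. The allocation rule cannot be found in the readable text, and the arithmetic is sound on its own assumptions. What does not stand is the step from a silence to a defect:

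- The 12-unit scenario has no positive evidence beyond the shape of a site list. That a name is a parent organisation is itself an inference.
- Clinics per name and organisation-level variance are not given, so the size of any effect is unknown. Clinic covariates in the model could also absorb some of the correlation.
- Part of the more alarming power loss in an uneven layout comes from the test chosen. For 60% v 68% at share 0, unweighted organisation means give .62 (ICC .01) and .39 (ICC .02). Weighting by clinic count on 9 df gives .78 and .52 with error near .05, although that weighting becomes too liberal at higher shares (about .10 at 50%).
- The plan itself presents its power as an illustration.

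**Conclusion.** No change to the plan follows. This is a missing detail that the analysts can fill from their own allocation records: the document is dated June 2016, and Section 6 expected implementation by about March 2015. Read as written, with clinics randomised singly, the clinic-level test keeps its nominal 5% error and this point leaves the power statement alone, so the effect is nil. Under joint allocation the error could reach about .16 or .22 at an assumed 50% organisation share, but nothing in the text supports that allocation. Replacing the clinic by the organisation as a precaution would cost power for no demonstrated benefit.

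The conclusion rests on the clinic having been the unit allocated, which the wording and the power figures both favour but do not prove. It would need revisiting only if the allocation records, Figure 3 or the note on CHC showed that clinics under one name shared an arm. It concerns this point alone: the plan gives neither the degrees of freedom nor the random coefficients at clinic level, so it does not certify the model in other respects.

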Statistical power. Segmented regression is a powerful statistical technique in diverse applications, but formal power analyses may not be feasible as estimates of the model parameters are not available prior to the study. We will meet or exceed the 12 points pre- and post-intervention used in similar segmented regression analyses, as is adequate to detect even modest effect. To illustrate our power to detect changes between study arms, we conducted a

power analysis using data from our current study. At 12 months post-intervention, 60%, 63% and 46% of control clinic patients and 68%, 76%, and 58% of intervention clinic patients were appropriately on statins, ACE, and both, respectively. We can detect differences of this magnitude between any two arms of the study with power of .95 to .99 if the intra-class correlation is .01, and power of .76 to .99 if the ICC is .02 with an alpha level of .05.

Additional analyses (Minimal support needed to achieve treatment thresholds): While our primary analyses will measure implementation impact as described above, we will also conduct secondary analyses, for both the patient health and guideline-based prescribing outcomes, in which we will define thresholds of intervention impact. Thresholds will be defined as a target percentage of clinic patients with (i) guideline-appropriate prescriptions; (ii) last LDL <100; and (iii) last systolic BP <135. Targets will be determined based on baseline data and in consultation with the SPREAD-NET advisory group, which includes CHC clinicians. We will then assess the minimal amount of implementation support needed to achieve threshold results. We anticipate based on our first study that these targets will be approximately (i) 75%; (ii) 70%; and (iii) 80%, respectively. Logistic regression will be used, with study arm (reference group = High support) predicting a binary outcome for threshold achieved by 12 months.

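### The secondary minimal-support analysis fits ordinary logistic regression to about 10 yes/no clinic values per arm, with no method for an arm in which no clinic, or every clinic, reaches the target

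*Combined protocol and SAP*

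**What the plan says.** The analysis is described in section 7a (Analysis Plan), under Additional analyses, and is labelled secondary. The outcome is set at clinic level: "Thresholds will be defined as a target percentage of clinic patients". The values are provisional: "Targets will be determined based on baseline data and in consultation with the SPREAD-NET advisory group", and "We anticipate based on our first study that these targets will be approximately (i) 75%; (ii) 70%; and (iii) 80%, respectively", for prescriptions, LDL and systolic BP in that order. The model is then given in one sentence: "Logistic regression will be used, with study arm (reference group = High support) predicting a binary outcome for threshold achieved by 12 months".

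No penalised, exact or other sparse-data method appears anywhere in the document, and no power or precision is given for this analysis. The three-level hierarchical model under Specific Aim 1 & 2 analyses serves the primary and maintenance analyses.

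Three definitions are left open:
- **Unit.** The clinic is implied but not named.
- **Outcome (i).** It is not tied to a drug measure. The Aim 1 text treats the drugs separately ("Separate analyses will be conducted for percent of patients with guideline-appropriate prescriptions for ACE/ARBs, statins (our primary outcomes"), and the Statistical power paragraph also reports a measure for both drugs together.
- **Timing.** Achievement by 12 months could mean status at month 12, or the target reached in any of the monthly extracts described in section 5b.

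**The concern.** A percentage of a clinic's patients, compared with a target, gives one binary value per clinic. Thirty clinics in three arms give about 10 values per arm; section 5d lists 29 clinics, which would leave one arm with 9. When every clinic in an arm has the same result, ordinary maximum likelihood gives no finite odds ratio for any contrast involving that arm. Because High is the reference, a uniform result in High removes both planned contrasts.

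This is the analysis the plan offers for its question about the minimum support needed. If the fit breaks down, a remedy would have to be chosen with the results in view. The plan also names no test, so the reported result could depend on a software default. In addition, reducing a clinic percentage to yes/no can discard much of its information.

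**Working it through.** **Inputs from the document.** 30 clinics and 3 arms (sections 4 and 5a); about 20,000 patients (5b); anticipated target 75%; ICC .01 and .02; alpha .05. Earlier-study rates at 12 months (Statistical power paragraph): for statins/ACE/both drugs, 60/63/46% in the control clinics; for the other group, "68%, 76%, and 58% of intervention clinic patients were appropriately on statins, ACE, and both, respectively".

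**Assumptions.** 10 clinics per arm; m = 20,000/30 = 667 patients per clinic; status at month 12; the cited pooled rates used as arm means; Medium halfway between Low and High; two-sided tests. Paired results are for ICC .01/.02.

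**1. The plan's own power figure.** The only stated power is for patient-level rates: "power of .95 to .99 if the intra-class correlation is .01, and power of .76 to .99 if the ICC is .02". With effective n per arm = 10 × 667/(1 + 666 × ICC) = 871/466, a two-proportion calculation gives .936/.721 for statins, >.999/.991 for ACE and .999/.957 for both. The .95 and .99 limits are met within about 2 points; .76 is not (.721). Eleven clinics per arm would give .955/.761, but the plan does not state that number. This gap concerns a different analysis and does not affect the present point.

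**2. What an extreme arm does to the fit.** Counts are in the order Low, Medium, High.
- 0/10, 4/10, 7/10: the Low v High log odds ratio runs to -23.4 (SE 15,241), while Medium v High stays finite (-1.25, SE 0.94).
- 3/10, 5/10, 10/10: both log odds ratios diverge.

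**3. How likely an extreme arm is.** Let q be the probability that a clinic reaches 75%, from a beta-binomial with m = 667, mean p and the given ICC. Then P(arm extreme) = q^10 + (1-q)^10, and P(at least one arm) = 1 - Π[1 - P(arm extreme)].

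Worked case, ACE at ICC .01: q = .0075, .1299 and .5979 for Low, Medium and High. The arm probabilities are .9278, .2486 and .0059, so the result is 1 - (.0722 × .7514 × .9941) = .946.

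| Arm means (Low/Medium/High) | ICC .01 | ICC .02 | ICC .05 (assumed) | ICC .10 (assumed) |
|---|---|---|---|---|
| Statins 60/64/68% | .999 | .954 | .53 | .19 |
| ACE 63/69.5/76% | .946 | .701 | .24 | .08 |
| All arms 68% | .837 | .469 | .12 | .04 |
| 68/72/76% | .480 | .207 | .05 | .02 |
| All arms 76% | .018 | .014 | .01 | .01 |
| Both drugs 46/52/58% | >.99 | >.99 | >.99 | .87 |

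The chance that High itself is extreme is .45/.19 if its mean is 68% and .006/.005 if it is 76%.

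**4. Effect of the target.** At 70%, statins 60/64/68% fall to .83/.49, but all arms at 76% rise to .73/.41. At 65%, statins 60/64/68% fall to .19/.08, but 68/72/76% rises to .94/.70.

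**5. Information lost by dichotomising (10 v 10 clinics).** For a t-test on clinic percentages, clinic variance = ICC·p(1-p) + p(1-p)(1-ICC)/667, df 18. For statins 60 v 68% at ICC .01, the variances are .002756 and .002499, SE = √(.005255/10) = .0229, and the noncentrality is .08/.0229 = 3.49. Power is .91; at ICC .02 it is .68. The likelihood-ratio test on the yes/no values, summed over all 11 × 11 tables, has power .04/.16. For ACE 63 v 76% the loss is small: >.99/.98 for the t-test against .98/.90.

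LDL and BP cannot be checked, because the document gives no rates for them.

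**The case against.** The strongest reply is that the high probabilities stack several assumptions. The .95 to .999 for statins needs a 75% target applied to statins, with Low held at the earlier study's control rate. Here every arm receives the toolkit and the EHR tools (section 4), so all arms may move up. The only quoted rate above 75% is ACE in intervention clinics (76%). The target is still to be set from baseline data, and a larger ICC lowers the risk sharply. All of this stands, and it is why no single probability should be taken from the table.

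A non-finite odds ratio is also not an empty result. It affects only contrasts with the extreme arm (all of them, if that arm is High). Counts such as 0/10 v 7/10 stay readable, and a likelihood-ratio or exact test can still be computed. This stands too, but the plan names none of these.

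The remedy is modest. Firth's test has lower power than the likelihood-ratio test (statins 60 v 68%: .01/.05 against .04/.16; ACE: .92/.80 against .98/.90), partly because the latter is liberal with samples this small. The added percentages partly overlap the segmented regression, although that model does not set each arm against the target.

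A reader might infer that this analysis is bound to fail, or that dichotomising always costs much power. The document supports neither: risk is .02/.01 with all arms at 76%, and for ACE the likelihood-ratio test loses little.

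**Conclusion.** The point holds as a gap in a secondary analysis. One binary value per clinic, about 10 per arm, is analysed by ordinary logistic regression with no provision for an arm at 0/10 or 10/10. Under scenarios built from the plan's own rates, ICCs and anticipated target, the chance of at least one such arm runs from about .01 to .999. That nearly fills the possible range (the floor for three arms of 10 is .006), so the figures show that the risk is real but do not estimate it. They rest on equal allocation, equal clinic sizes, month-12 status and a beta-binomial spread between clinics, and the final target could move them either way.

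The clinic as unit and 10 per arm are sound inferences, not stated text. Nor does the document show that outcome (i) must be split by drug with separate targets: a statin, an ACE/ARB or a both-drugs measure would each fit the wording, so the plan needs to say which it means. A reader might extend the problem to the trial's main result; the primary segmented regression does not use this dichotomy and is unaffected. The change should be made, at modest priority.

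**What to change.** Amend the Additional analyses paragraph as follows:

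- Name the clinic as the unit of analysis.
- State which measure the target in (i) applies to: statin, ACE/ARB or both.
- State whether achievement by 12 months means status at month 12.
- Keep the clinic-level yes/no analysis and report the counts per arm, but fit it by Firth logistic regression (penalised likelihood-ratio tests and intervals) or exact logistic regression in place of ordinary logistic regression.
- Beside it, report each arm's baseline-adjusted 12-month clinic percentage with a 95% CI and its difference from High, shown against the target.

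The percentages are the more informative comparison between arms, but they do not settle on their own whether an arm has reached the target. Without baseline adjustment, an arm truly at 76% has a CI half-width of 3.0/4.1 points (ICC .01/.02), and its interval lies above 75% with probability only .10/.07.

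The cost is wording and slightly more analysis on the same data. Firth estimates are shrunken, and intervals from either method are wide: for 0/10 v 3/10 the Firth odds ratio is .10 (95% CI .001 to 1.29), and the exact interval is 0 to 2.26. Neither method recovers the power lost by dichotomising.
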